4.2. Study Endpoints

The endpoints of the study are listed below:

- Primary endpoint
 - Objective response and long-term stable disease rate
- Secondary endpoints
 - Objective response rate
 - Long-term stable disease rate
 - Duration of response
 - Progression-free survival
 - Overall survival
 - Safety
- Exploratory endpoints
 - Pomalidomide PK characterization

4.3. Stratification, Randomization and Blinding

This is an open-label, single therapy study. Treatment assignment does not require randomization, blinding, or stratification.

4.4. Overall Study Design and Plan

[figure not shown]
Each tumor type/disease indication incorporates the Simon's Optimal Two-stage study design incorporating the following parameters: significance level of 5%, 90% power and a lower and upper boundary of interest of 10% and 40%, respectively, of the primary endpoint. Based on these boundaries, each tumor type/disease indication will enroll up to 20 subjects eligible for the primary endpoint; 9 in stage one and 11 in stage two. Subjects not eligible for the primary endpoint, ie, not contained within the Response Population, If the number of subjects observed with either an OR or long-term SD according to central response review is ≥ 2 , then enrollment shall continue into stage two; otherwise enrollment will close to that specific tumor type/disease

indication. At the end of stage two, if ≥ 5 out of 20, ie, the target ORSDR $\geq 25\%$, of the subjects enrolled across stage one and stage two combined are observed as having an OR or long-term SD then the treatment will be declared positive in that given tumor type/disease indication; otherwise the treatment will be considered negative in that given tumor type/disease indication (

Figure 2).

If, in a given tumor type/disease indication, by the time the eighteenth subject becomes evaluable for the primary endpoint and only two subjects have been observed across stage 1 and stage 2 combined as having either a OR or long-term SD then enrollment to that tumor type/disease indication will be stopped due to a lack of efficacy.

Figure 1: Overall Study Design

[figure not shown]

ICF=informed consent form, IAF=informed assent form, MRI=magnetic resonance imaging, OS=overall survival, PD=disease progression, PFS=progression-free survival, SAE=serious adverse event, SPM=second primary malignancy.

*From last subject enrolled

**Subjects without a PD at time of treatment discontinuation will continue to be followed for MRI tumor assessment (every 6 months for the first year from treatment discontinuation, then annually thereafter).

Figure 2: Simon’s Optimal Two-stage Parallel Phase 2 Study Design

DIPG=diffuse intrinsic pontine glioma, OR=objective response, PD=progressive disease, LTSD= Long-term stable disease.

6. STATISTICAL METHODOLOGY FOR EFFICACY

Tables will be provided to describe the efficacy endpoints for the Response Population, Safety Population and ITT Population; the ITT Population will only be invoked if at least one of the subjects enrolled does not receive a single dose of pomalidomide. In addition, analysis of the primary endpoint, ORSDR, will be based primarily on the Response Population and decision making such as go/no-go into stage 2 will be based on the analysis using this analysis population. Tables will present data by tumor type/disease indication separately and not in aggregate. Listings will display response assessment data for the ITT Population.

Efficacy endpoints reliant on disease assessments will be based on the independent central response assessments.

In instances where disease assessments are reliant on measurements being collected over a series of days, the last day a measurement is recorded will be used as the date for documentation of the CR, PR, SD or PD.

Missing efficacy data will not be imputed.

6.1. Analysis of Primary Efficacy Endpoint

6.1.1. Objective Response and Long-term Stable Disease Rate

The ORSDR is defined as the percentage of subjects that achieve either a CR, PR or SD maintained for ≥ 6 cycles (≥ 3 cycles for the DIPG tumor type/disease indication) as their best response, divided by the total number of subjects available for the analysis within the given population, eg, subjects contained within the Response Population (primary analysis), the ITT Population, and the Safety Population as outlined within Section 5 of this SAP. The ITT Population will not be used should all enrolled subjects have received at least one dose of study drug. Non-responder subjects are considered subjects with a PD as best response, subjects not having a postbaseline assessment or subjects having not evaluable recorded on their postbaseline assessment(s). The corresponding 2-sided, 95% Clopper-Pearson confidence interval (CI) will also be provided.

Calculation of SD duration starts at the time of first dose of pomalidomide and continues until the date of the first observation of PD is recorded or death due to any cause, regardless of whether the subject achieves a CR and/or PR within that period, or until the date of the last disease assessment if no PD or death is recorded; if the difference is ≥ 6 cycles (≥ 3 cycles for the DIPG tumor type/disease indication), ie, the subject has not had a documented PD before Cycle 7, Day 1 (Cycle 4, Day 1 for the DIPG tumor type/disease indication) and has completed 6 cycles of pomalidomide (3 cycles for the DIPG tumor type/disease indication), then the SD will be considered as being maintained for ≥ 6 cycles (≥ 3 cycles for the DIPG tumor type/disease indication).

For identification of PD for this SD duration calculation, PD is classified as a PD as observed during a response assessment (both during the Treatment Period and the Follow-up Period if applicable); the first time this occurrence is observed is selected as the PD date.

Disease assessments recorded on or after start of a new anticancer therapy will not be considered, nor will disease assessments reported after a PD has been observed.

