2. STUDY OBJECTIVES AND ENDPOINTS

Table 1: Study Objectives

Primary Objective(s)
The primary objective of the study is: 
• To identify potential tumor type(s) for further development by establishing the preliminary efficacy of pomalidomide in children and young adults with recurrent or progressive primary brain tumors within four distinct tumor types.
Secondary Objective(s)
The secondary objectives are: 
• To evaluate the safety (type and rate of treatment-related toxicity) of pomalidomide within the study populations.• To estimate the long-term efficacy of pomalidomide treatment.
Exploratory Objective(s)
The exploratory objectives are: 
• To assess the PK of pomalidomide in children and young adults with recurrent or progressive primary brain tumors.

PK= Pharmacokinetics.

Table 2: Study Endpoints

Endpoint	Name	Description	Timeframe
Primary	Objective response and long-term stable disease rate	Total number of subjects achieving an OR (either CR or PR) or a long-term SD under study treatment, among total subjects evaluable for analysis per stratum	Cycle 1, Day 1 to completion of Cycle 6 (completion of Cycle 3 for DIPG)
Secondary	Objective response rate	Total number of subjects achieving an OR (either CR or PR) under study treatment, among total subjects evaluable for analysis per stratum	Cycle 1, Day 1 of Treatment Period to end of Follow-up Period
	Long-term stable disease rate	Total number of subjects achieving a long-term SD under study treatment, among total subjects evaluable for analysis per stratum	Cycle 1, Day 1 to completion of Cycle 6 (completion of Cycle 3 for DIPG)
	Duration of response	The time from first achievement of CR or PR under study treatment, whichever occurs first, until first documentation of progressive disease (PD) or death of any cause	Cycle 1, Day 1 of Treatment Period to end of Follow-up Period
	Progression-free survival	The time from enrollment until first documentation of PD and/or death of any cause	Cycle 1, Day 1 of Treatment Period to end of Follow-up Period
	Overall Survival	The time from enrollment until death of any cause	Cycle 1, Day 1 of Treatment Period to end of Follow-up Period
	Safety	Type, frequency, and severity of AEs and relationship to study drug	Signing of informed consent form (ICF)/informed assent form (IAF) until the end of Follow-up Period

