9.3. Sample Size and Power Considerations

Under Simon's Optimal two-stage design with a 5% significance level and 90% power, assuming a lower boundary of interest in the response rate of 10% and an upper boundary of interest in the

response rate of 40%, a total of 20 subjects evaluable for the primary endpoint (ie, Response Population) are required per stratum; 9 per stratum in Stage 1 and an additional 11 per stratum in Stage 2.

Enrollment will proceed as follows:

1. Stage 1: Nine subjects will be enrolled into each of the strata.
2. Stage 2: If during Stage 1, ≥ 2 subjects in a given stratum achieve either an OR (either CR or PR) within the first 6 cycles of treatment (within 3 cycles for DIPG) or a long-term SD, an additional 11 subjects shall be enrolled to that stratum; otherwise no additional subjects will be enrolled.
3. If a total of 5 or more subjects across all 20 subjects in a given stratum (Stage 1 and 2) evaluable for the primary endpoint are observed as having either an OR (either CR or PR) within the first 6 cycles of treatment (within 3 cycles for DIPG) or long-term SD, pomalidomide will be considered effective in that disease indication.

Up to 80 subjects (36 subjects in Stage 1 and 44 subjects in Stage 2) will be included should all strata enroll the maximum number of subjects (ie, 20 per stratum), assuming no subjects are replaced.

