9.6. Efficacy Analysis

Objective Response and Long-term Stable Disease Rate

Objective response and long-term SD rate (ORSDR), is defined as the total number of subjects achieving either an OR (either CR or PR) within the first 6 cycles of treatment (within 3 cycles for DIPG) or a long-term SD (SD maintained for ≥ 6 cycles [≥ 3 cycles for DIPG]), over the total number of subjects evaluable for analysis. Evaluable is defined as a subject completing at least one cycle of study therapy or discontinuing treatment earlier due to a PD. Subjects completing at least one cycle of study therapy but not having at least one subsequent (post-baseline) disease assessment will be considered a non-responder. The corresponding Clopper Pearson 95% confidence interval (CI) shall be calculated for each rate per stratum. Each stratum will be analyzed separately. Analysis of this endpoint will be based on the Response Population, with secondary analyses based on the ITT Population and/or Safety Population.

Objective Response Rate

The ORR is defined as the total number of subjects achieving an OR (either CR or PR), over the total number of subjects evaluable for the analysis. Disease responses occurring after start of a new anticancer therapy shall not be considered. Each stratum will be analyzed separately. Analysis of this endpoint will be based on the ITT Population and/or Safety Population.

Long-term Stable Disease Rate

The long-term SD rate is the proportion of subjects achieving long-term SD, defined as a SD maintained for ≥ 6 cycles (≥ 3 cycles for DIPG), over the total number of subjects evaluable for the analysis. The corresponding Clopper Pearson 95% CI shall be calculated for each rate per stratum. Each stratum shall be analyzed separately. Analysis of this endpoint will be based on the ITT Population and/or Safety Population.

Duration of Response

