6.5. Interim Analysis

Each tumor type/disease indication incorporates the Simon's Optimal Two-stage study design, using a 5% significance level, 90% power, and a lower and upper boundary of 10% and 40%, respectively, for the primary endpoint. For stage one to be evaluated in a given tumor type/disease indication, there must be 9 subjects eligible for the primary endpoint analysis. Subjects If at least 2 subjects are observed as having as either a CR, PR or long-term SD according to central response review, ie, at least 2/9 ($\geq 22\%$), then enrollment in to stage two will continue as planned; otherwise that tumor type/disease indication will be closed to enrollment and the treatment in that tumor type/disease indication considered inefficacious.

If, in a given tumor type/disease indication, none of the first 8 subjects evaluable for the primary endpoint have an OR or long-term SD before the ninth subjects is enrolled, that particular tumor type/disease indication will close to enrollment due to early identification of futility. Similar, if at the time of the interim analysis the required number of subjects observed with an OR or long-term SD is 5 or more, then the enrollment to that given tumor type/disease indication may to stopped due to the required efficacy across stage 1 and stage 2 to declare the study positive in that tumor type/disease indication having been demonstrated early. Each tumor type/disease

indication is run in parallel to each other meaning the interim analysis per tumor type/disease indication may be conducted at different times, as and when the data becomes available for analysis.

CELGENE PROPRIETARY INFORMATION

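### The SAP's primary endpoint omits the protocol's time limit on objective response, so a rare late response could turn 4/20 into 5/20

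*SAP*

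**What the plan says.** Protocol 9.6 defines the numerator of the primary endpoint as subjects "achieving either an OR (either CR or PR) within the first 6 cycles of treatment (within 3 cycles for DIPG"), or with SD lasting at least 6 (3) cycles. The Protocol Summary, 3.1 and 9.3 carry the same limit. Table 2 sets the primary timeframe as "Cycle 1, Day 1 to completion of Cycle 6 (completion of Cycle 3 for DIPG") and refers to response while on study treatment. The same table runs the secondary ORR to the end of follow-up, so the protocol pairs a windowed primary endpoint with an open-ended secondary one.

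SAP 6.1.1 reads "The ORSDR is defined as the percentage of subjects that achieve either a CR, PR or SD maintained for ≥ 6 cycles" (3 for DIPG), taken as best response. SAP 4.1 and 4.4 give no window for response either. The interim rule in SAP 6.5 is "If at least 2 subjects are observed as having as either a CR, PR or long-term SD according to central response review". The assessments SAP 6.1.1 sets aside are those on or after new anticancer therapy and those after a PD. For long-term SD it also requires that the subject has completed 6 (3) cycles of drug.

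Under protocol 6.3.3, subjects who stop without progression are scanned every 6 months in the first year and then annually, with central reading. SAP section 12 places the primary analysis after the last treated subject's 28-day safety visit and reruns all outputs when follow-up ends.

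**The concern.** The Simon boundaries were set for an endpoint that closes at the end of Cycle 6 (3). As written, the SAP's response component has no closing date. A subject who stopped early without progression is not long-term SD under SAP 6.1.1, but a PR on an off-treatment scan months later would make that subject a success. The final rule, "If a total of 5 or more subjects across all 20 subjects in a given stratum", is then applied to a count that can still grow after the protocol's window has shut. What is at stake is the error rate attached to a positive call in a stratum, and a primary result that could differ between the primary and end-of-study analyses.

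**Working it through.** **1. Who is counted differently.** This takes SAP 6.1.1 against protocol 9.6, with SD maintained for at least 6 (3) cycles read as requiring those cycles.

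| Subject | Protocol 9.6 | SAP 6.1.1 |
|---|---|---|
| CR/PR within 6 (3) cycles | success | success |
| Completes 6 (3) cycles without PD, first CR/PR later | success (long-term SD) | success |
| PD before any CR/PR, within 6 (3) cycles | not a success | not a success |
| Stops early, no PD or new therapy, first CR/PR after the window | not a success | success |

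Only the last row differs. There is time for it to occur: the window is 6 × 28 = 168 days (3 × 28 = 84 for DIPG), while treatment of other subjects may run 24 × 28 = 672 days before the primary analysis.

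**2. The plan's own design.** Inputs are "two-stage design with a 5% significance level and 90% power" and "9 per stratum in Stage 1 and an additional 11 per stratum in Stage 2" (protocol 9.3) and "a lower and upper boundary of interest of 10% and 40%, respectively, of the primary endpoint" (SAP 4.4). The rules are to continue at 2 or more of 9 and to call success at 5 or more of 20.

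P(success) = Σ over x = 2 to 9 of P(X1 = x) × P(X2 ≥ 5 − x), with X1 ~ Bin(9, p) and X2 ~ Bin(11, p).

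At p = 0.10:
- x = 2: 0.1722 × 0.0896 = 0.0154
- x = 3: 0.0446 × 0.3026 = 0.0135
- x = 4: 0.00744 × 0.6862 = 0.0051
- x ≥ 5: 0.0009

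The sum is 0.0349. At p = 0.40 the same formula gives 0.9018. A full search for the optimal design returns the same 9 + 11 subjects and the same boundaries, so the stated design reproduces.

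**3. One subject at each boundary** (Clopper-Pearson 95% CI).
- 4/20 = 20.0% (5.7 to 43.7) becomes 5/20 = 25.0% (8.7 to 49.1), and the conclusion changes.
- 1/9 = 11.1% (0.3 to 48.2) becomes 2/9 = 22.2% (2.8 to 60.0). Enrollment has already closed.

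**4. Effect on type I error.** Let f be the chance that a window non-responder later counts under the SAP. The documents give no value, so f is an assumption, taken as independent between subjects. Stage 1 is decided on the window count and the final result on the SAP count. With q = p + (1 − p)f:

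P(success) = Σ over x = 2 to 9 and y = 0 to 9 − x of P(Bin(9, p) = x) × P(Bin(9 − x, f) = y) × P(Bin(11, q) ≥ 5 − x − y).

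| f | Type I error at p = 0.10 |
|---|---|
| 0 | 0.0349 |
| 1% | 0.0443 |
| 2% | 0.0543 |
| 3% | 0.0647 |
| 5% | 0.0861 |

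The nominal 5% is crossed between f = 1% and f = 2%.

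**5. Chance that 4/20 is turned.** P(4/20 after passing Stage 1) at p = 0.10 is 0.0367 + 0.0171 + 0.0023 = 0.0561. At least one of the 16 non-responders flips with probability 1 − (1 − f)^16.
- f = 1%: 0.0561 × 0.1485 = 0.8%
- f = 2%: 0.0561 × 0.2762 = 1.6%
- f = 5%: 0.0561 × 0.5599 = 3.1%

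At p = 0.40 the boundary probability is 2.2%, and f = 2% gives 0.022 × 0.2762 = 0.6%. The rise in step 4 at f = 2% (0.0543 − 0.0349 = 0.0194) is a little larger than 1.6% because it also includes strata at 3/20 or fewer with two or more flips.

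**The case against.** Four points weigh against a stronger claim.

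- **The early stopper may already be a protocol success.** Protocol 6.4.1.7 and Appendix C treat anyone with neither response nor progression by the end of Cycle 6 (3) as long-term SD and do not mention completed cycles. Read literally, a later PR would bring the SAP into line with the protocol. A reader might infer that such a subject is plainly a protocol failure; that rests on protocol 9.6 and on a completed-cycles condition that only the SAP states. This point stands. The protocol is ambiguous and needs reconciling too.
- **The SAP does not affirmatively adopt late responses.** Its mention of follow-up assessments in 6.1.1 concerns identifying progression. That is fair: this is an omission. But the listed exclusions do not remove an off-treatment response, so a programmer following the text would count it.
- **Stage 1 is not re-decided.** A reader might infer that a stratum closed at 1/9 could later change status. Neither document reopens a closed stratum, SAP 6.5 already labels it inefficacious, and one late response gives 2/9, short of the five needed. Only the reported rate would move.
- **Being at a boundary is not the same as a changed result.** At a 10% true rate, 1/9 has probability 38.7% and 4/20 has 5.6%. A reader might take these as the size of the problem. They must be multiplied by the chance of a late response, as in step 5.

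Protocol 9.8 also states the interim rule without the window. It gives a decision rule and not the endpoint definition, so it does not displace 9.3 or 9.6.

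**Conclusion.** The SAP and protocol define the primary endpoint differently, and the SAP should be corrected. The practical effect is confined to early stoppers without progression or new therapy whose first CR or PR falls after the window. They should be few, since most window non-responders can be expected to have progressed. The live decision point is 4/20 against 5/20. At an assumed f of 2%, type I error at 10% goes from 0.035 to about 0.054, and the chance that a stratum sitting at 4/20 is turned is 1.6% at a 10% true rate and 0.6% at 40%. These figures depend on the assumed f, on independence between subjects, and on reading protocol 9.6 as requiring SD to last the full 6 (3) cycles. The documents do not support a claim that closed strata could be reopened or that a changed result is likely.

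**What to change.** In SAP 4.1, 4.4, 6.1.1 and 6.5, define an ORSDR success as either of:

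- CR or PR documented at or before the end-of-Cycle-6 assessment (end of Cycle 3 for DIPG), with the scheduled Cycle 7 (Cycle 4) Day 1 scan counted as that assessment. The scan must be named because for DIPG it is the first scheduled post-baseline scan.
- SD maintained for at least 6 (3) cycles, regardless of any later CR or PR.

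Determine best response for ORSDR inside that window and leave later responses to ORR. Simply adding that later responses count only in ORR would not be safe. SAP 6.1.1 requires SD as best response, so a subject with SD through Cycle 6 and a first PR at Cycle 10 could lose success status.

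In the same revision, reconcile the SAP's completed-cycles condition for long-term SD with protocol 6.4.1.7 and Appendix C, so that an early stopper without progression is classified the same way in both documents.

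The cost is a short rewording in four SAP sections plus that reconciliation. No new data, scans or subjects are needed. With the protocol window restored, the design's exact error rates of 0.0349 and 0.9018 power apply as planned.
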